**Table 22. ALT or AST Increase**

ALT or AST increase	Management
Grade 1 (ULN - 3.0 x ULN if baseline was normal; 1.5 - 3.0 x baseline if baseline was abnormal) or Grade 2 ( $>3.0 - 5.0 \times$ ULN if baseline was	Dose modification not required.

normal; >3.0 - 5.0 x baseline if baseline was abnormal)																														
Transient Grade 2	
Liver testing, including ALT, AST, ALP, total bilirubin, direct bilirubin, gamma-glutamyl transferase, and creatine kinase, should be repeated within 2 to 4 days to confirm the abnormality and to determine if it is increasing or decreasing.
																													
Persistent or Recurrent Grade 2 that does not resolve with maximal supportive measures within 7 days to baseline or Grade 1, or Grade 3	
Suspend dose until toxicity resolves to baseline or Grade 1. Resume at next lower dose.
 
If the abnormality persists or worsens, clinical and laboratory monitoring and evaluation for possible causes of abnormal liver tests, should be initiated by the investigator. At a minimum, this evaluation should include physical examination and a thorough medical history, including symptoms, recent illnesses (for example, heart failure, systemic infection, hypotension, or seizures), history of concomitant medications (including over-the-counter, herbal and dietary supplements, history of alcohol drinking and other substance abuse). In addition, the evaluation should include a blood test for prothrombin time (PT-INR); serological tests for viral hepatitis A, B, C, E, autoimmune hepatitis; and an abdominal imaging study (for example, ultrasound or CT scan).
 
Based on the patient's history and initial evaluation results, further testing should be considered in consultation with the Sponsor-Investigator, including tests for hepatitis D virus (HDV), cytomegalovirus (CMV), Epstein-Barr virus (EBV), acetaminophen levels, acetaminophen protein adducts, urine toxicology screen, Wilson's disease, blood alcohol levels, urinary ethyl glucuronide, and serum phosphatidylethanol, as well as additional laboratory testing from the list below as indicated based on the patient's medical history, risk factors and exposures. Based on the circumstances and the investigator's assessment of the participant's clinical condition, the investigator should consider referring the participant for a hepatologist or gastroenterologist consultation, magnetic resonance cholangiopancreatography (MRCP), endoscopic retrograde cholangiopancreatography (ERCP), cardiac echocardiogram, and/or a liver biopsy:
 
  
 Hematology	Clinical Chemistry	
   
 Hemoglobin	Total bilirubin	
 
 Hematocrit	Direct bilirubin	
 
 Erythrocytes (RBCs - red blood cells)	Alkaline phosphatase (ALP)	
 
 Leukocytes (WBCs - white blood cells)	Alanine aminotransferase (ALT)	
 
 Differential:	Aspartate aminotransferase (AST)	
 
 Neutrophils, segmented	Gamma-glutamyl transferase (GGT)	
 
 Lymphocytes	Creatine kinase (CK)	
 
 Monocytes	Other Chemistry	
 
 Basophils	Acetaminophen	
 
 Eosinophils	Acetaminophen protein adducts	
 
 Platelets	Alkaline phosphatase isoenzymes	
 
 Cell morphology (RBC and WBC)	Ceruloplasmin	
 
 Coagulation	Copper	
 
 Ethyl alcohol (EtOH)	
  
	Hematology	Clinical Chemistry	Hemoglobin	Total bilirubin	Hematocrit	Direct bilirubin	Erythrocytes (RBCs - red blood cells)	Alkaline phosphatase (ALP)	Leukocytes (WBCs - white blood cells)	Alanine aminotransferase (ALT)	Differential:	Aspartate aminotransferase (AST)	Neutrophils, segmented	Gamma-glutamyl transferase (GGT)	Lymphocytes	Creatine kinase (CK)	Monocytes	Other Chemistry	Basophils	Acetaminophen	Eosinophils	Acetaminophen protein adducts	Platelets	Alkaline phosphatase isoenzymes	Cell morphology (RBC and WBC)	Ceruloplasmin	Coagulation	Copper	Ethyl alcohol (EtOH)
Hematology	Clinical Chemistry																													
Hemoglobin	Total bilirubin																													
Hematocrit	Direct bilirubin																													
Erythrocytes (RBCs - red blood cells)	Alkaline phosphatase (ALP)																													
Leukocytes (WBCs - white blood cells)	Alanine aminotransferase (ALT)																													
Differential:	Aspartate aminotransferase (AST)																													
Neutrophils, segmented	Gamma-glutamyl transferase (GGT)																													
Lymphocytes	Creatine kinase (CK)																													
Monocytes	Other Chemistry																													
Basophils	Acetaminophen																													
Eosinophils	Acetaminophen protein adducts																													
Platelets	Alkaline phosphatase isoenzymes																													
Cell morphology (RBC and WBC)	Ceruloplasmin																													
Coagulation	Copper																													
	Ethyl alcohol (EtOH)																													

	Prothrombin time, INR (PT-INR)	Haptoglobin
	Serology	Immunoglobulin IgA (quantitative)
	Hepatitis A virus (HAV) testing:	Immunoglobulin IgG (quantitative)
	HAV total antibody	Immunoglobulin IgM (quantitative)
	HAV IgM antibody	Phosphatidylethanol (PEth)
	Hepatitis B virus (HBV) testing:	Urine Chemistry
	Hepatitis B surface antigen (HBsAg)	Drug screen
	Hepatitis B surface antibody (anti-HBs)	Ethyl glucuronide (EtG)
	Hepatitis B core total antibody (anti-HBc)	Other Serology
	Hepatitis B core IgM antibody	Anti-nuclear antibody (ANA)
	Hepatitis B core IgG antibody	Anti-smooth muscle antibody (ASMA)
	HBV DNA	Anti-actin antibody
	Hepatitis C virus (HCV) testing:	Epstein-Barr virus (EBV) testing:
	HCV antibody	EBV antibody
	HCV RNA	EBV DNA
	Hepatitis D virus (HDV) testing:	Cytomegalovirus (CMV) testing:
	HDV antibody	CMV antibody
	Hepatitis E virus (HEV) testing:	CMV DNA
	HEV IgG antibody	Herpes simplex virus (HSV) testing:
	HEV IgM antibody	HSV (Type 1 and 2) antibody
	HEV RNA	HSV (Type 1 and 2) DNA
	Microbiology	Liver kidney microsomal type 1 (LKM-1) antibody
	Culture:	-
	Blood	-
	Urine	-
Grade 2 or 3 (>5.0 - 20.0 x ULN if baseline was normal; >5.0 - 20.0 x baseline if baseline was abnormal) with total bilirubin >2 x ULN, in the absence of	Discontinue abemaciclib and contact Sponsor-Investigator.	

cholestasis OR Grade 4 ( $>20.0 \times$ ULN if baseline was normal; $>20.0 \times$ baseline if baseline was abnormal)	
---	--

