## **6. DOSING DELAYS/DOSE MODIFICATIONS**

Dose delays and modifications will be made as indicated in the following table(s). The descriptions and grading scales found in the revised NCI Common Terminology Criteria for Adverse Events (CTCAE) version 5.0 will be utilized for dose delays and dose modifications. A copy of the CTCAE version 5.0 can be downloaded from the CTEP website [http://ctep.cancer.gov/protocolDevelopment/electronic\\_applications/ctc.htm](http://ctep.cancer.gov/protocolDevelopment/electronic_applications/ctc.htm).

Any patient who receives protocol treatment will be evaluable for toxicity. Each patient will be assessed for the development of toxicity according to the Study Calendar (Section 10). Toxicity will be assessed according to the NCI Common Terminology Criteria for Adverse Events (CTCAE), version 5.0. Dose adjustments should be made according to the system showing the greatest degree of toxicity. The dose delays and modifications described here are requirements, but re-escalation of abemaciclib dose is permitted per discretion of the treating investigator if there is improvement in the adverse event for which the dose was initially reduced. Investigators are encouraged to contact the Sponsor-Investigative team with any questions.

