**Table 4. Abemaciclib Dosing Modifications**

Abemaciclib Dosing Modifications		
Dose Level	Monotherapy	Combination therapy
1	200mg BID	150mg BID
-1	150mg BID	100mg BID
-2	100mg BID	50mg BID
-3	50mg BID	Discontinue

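### The Table 22 stopping rule names Grade 2 or 3 ALT/AST elevation but prints only the Grade 3 range, so it can be misread as excluding Grade 2 with raised bilirubin

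*Combined protocol and SAP*

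**What the plan says.** Section 6 adopts CTCAE version 5.0 grading for dose delays and modifications and makes the modifications binding. Table 22 (section 6.2) then sets the abemaciclib action for raised ALT or AST in four rows.

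- **Row 1, Grade 1 or Grade 2.** No dose modification. Grade 2 is >3.0–5.0 × ULN for a normal baseline and ">3.0 - 5.0 x baseline if baseline was abnormal".
- **Row 2, transient Grade 2.** A liver panel that includes total and direct bilirubin "should be repeated within 2 to 4 days to confirm the abnormality".
- **Row 3, Grade 2 that recurs or does not settle within 7 days, or Grade 3.** "Suspend dose until toxicity resolves to baseline or Grade 1. Resume at next lower dose". No range is printed for either grade.
- **Row 4, discontinuation.** Abemaciclib stops and the Sponsor-Investigator is contacted. The trigger reads "Grade 2 or 3 (>5.0 - 20.0 x ULN if baseline was normal" and continues ">5.0 - 20.0 x baseline if baseline was abnormal) with total bilirubin >2 x ULN, in the absence of" cholestasis. The alternative trigger is Grade 4, which has its own range (>20.0 ×) and no bilirubin condition.

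Neither row 1 nor row 3 mentions bilirubin as an exception.

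**The concern.** Row 4 is the protocol's abemaciclib stopping rule for possible drug-induced liver injury. It attaches one range to two grades, and that range lies wholly above Grade 2 as row 1 defines it. A site that takes the numbers as the trigger could conclude that a Grade 2 elevation with bilirubin >2 × ULN does not reach row 4.

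The action would then differ. On the label, abemaciclib ends. On the printed numbers, it may continue under row 1, or be suspended and resumed one level lower under row 3. For monotherapy, Table 4 ("Abemaciclib Dosing Modifications") makes that level 150 mg BID. Section 6 adds that "re-escalation of abemaciclib dose is permitted per discretion of the treating investigator if there is improvement in the adverse event", so a return towards 200 mg BID would also be open if the event improved.

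**Working it through.** There is no design figure to reproduce here. The check compares the printed ranges and then asks which reading the rest of the protocol supports.

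**1. Ranges side by side (Table 22)**

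| Place | Grade label | Printed range (× ULN, or × baseline if abnormal) |
|---|---|---|
| Row 1 | Grade 2 | >3.0–5.0 |
| Row 3 | Grade 2 or Grade 3 | none |
| Row 4, first branch | Grade 2 or 3 | >5.0–20.0 |
| Row 4, second branch | Grade 4 | >20.0 |

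**2. Overlap.** The overlap of (3.0, 5.0] with (5.0, 20.0] is min(5.0, 20.0) − max(3.0, 5.0) = 5.0 − 5.0 = 0, on both scales. No Grade 2 value lies in the range printed in row 4. By itself this shows only that the printed range is the Grade 3 band and that the Grade 2 band is not repeated there.

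**3. A case where the readings part.** Normal baseline, ALT 4 × ULN, total bilirubin 2.5 × ULN, no cholestasis.
- Range read as defining Grade 3 only: 4 is in (3.0, 5.0], so the event is Grade 2, row 4 applies and abemaciclib is discontinued.
- Range read as governing both grades: 4 is not in (5.0, 20.0], so row 4 does not apply. Row 1 (no change) or, if the event persists or recurs, row 3 (suspend, then resume lower) would govern.

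**4. Abnormal baseline.** Section 3.1.9 admits abemaciclib patients with ALT/AST up to 1.5 × ULN. At that limit Grade 2 runs from 3.0 × 1.5 = 4.5 to 5.0 × 1.5 = 7.5 × ULN, so the affected band can reach 7.5 × ULN.

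**5. Which reading is intended**
- The row names Grade 2. If the range governed both grades, that word could never apply.
- In row 1, and in the Grade 4 branch of row 4, each parenthesis defines the grade just before it. Read the same way, the row 4 range defines Grade 3, which has no printed range anywhere else in the table.
- Section 6 adopts CTCAE v5.0 grades for dosing decisions, and row 3 already asks sites to act on the grade without a range.
- The DLT list in section 7.3 includes ALT or AST >3 × ULN with bilirubin >2 × ULN and no cholestasis. Section 7.2.8 makes ALT or AST >3 × ULN with bilirubin >2 × ULN an event of special interest for all participants. Both are on the ULN scale, so they match the lower bound of Grade 2 exactly only for a normal baseline, but they point the same way.

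**6. Whether another rule already settles the dose.** None does expressly.
- Table 24 excludes hepatotoxicity, and Table 17 directs atezolizumab only.
- Sections 7.2.8 and 7.3 classify and report events; they do not direct an individual patient's abemaciclib dose.
- The sentence "Dose adjustments should be made according to the system showing the greatest degree of toxicity" favours the stricter action but compares organ systems. It does not rank the rows of one table.
- Section 5.4 provides for removal for unacceptable adverse events but gives no liver threshold.

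**The case against.** The strongest reply is that this is a copy-edit and the row has one sensible reading. The parenthesis belongs to Grade 3 by the table's own pattern. The rival reading requires a site to disregard an explicit grade label. The missing bilirubin exception in row 1 proves nothing, because row 3 also covers Grade 3 without such an exception, yet row 4 plainly overrides it when bilirubin is >2 × ULN; the same logic carries Grade 2 from row 1 to row 4. Investigators are also encouraged to contact the Sponsor-Investigator's team with questions.

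Most of this stands. A reader might infer that Table 22 contradicts itself, or that the plan lets patients with Grade 2 elevation and raised bilirubin stay on abemaciclib. The documents support neither inference: once the parenthesis is attached to Grade 3, rows 1 and 4 are compatible and Grade 2 is covered.

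What the reply does not remove is that the reader has to work this out. Row 4 is the only place in the table where two grades share one range, and it is a binding discontinuation threshold. Row 1 gives an unqualified no-change instruction for the same ALT/AST value.

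**Conclusion.** The point holds as a minor defect: a stopping threshold for possible drug-induced liver injury can be misread, although its intent can be recovered. The affected zone is the whole Grade 2 band (>3.0–5.0 × ULN, or × baseline if abnormal) with total bilirubin >2 × ULN and no cholestasis. The documents give no incidence for that combination, so no number of cases is claimed.

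Even on the wrong reading, harm is limited. Repeat liver tests including bilirubin are due within 2 to 4 days, Grade 2 unresolved within 7 days leads to suspension, the event is of special interest for every participant, and section 5.4 covers removal for unacceptable toxicity. Endpoints, power and DLT classification are not affected. The conclusion assumes that the row is printed as it appears in the available text. The same range on both the ULN and the baseline scale makes a reading error in the text unlikely.

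**What to change.** In the last row of Table 22, give each grade its own range:

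> Grade 2 (>3.0–5.0 × ULN if baseline was normal; >3.0–5.0 × baseline if abnormal) or Grade 3 (>5.0–20.0 × ULN if baseline was normal; >5.0–20.0 × baseline if abnormal) with total bilirubin >2 × ULN, in the absence of cholestasis, OR Grade 4 (existing range).

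A short cross-reference from the Grade 2 and Grade 3 rows to this row would help but is optional.

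The cost is one table row in the next amendment. No new test or data item is needed, because the repeat panel in Table 22 already includes total and direct bilirubin. Nothing in section 13 changes.

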**Table 23. Hematologic Toxicity**

Hematologic Toxicity	Management
(management overview)	Hematologic toxicities including neutropenia, leukopenia, anemia, and thrombocytopenia have been observed in patients treated with abemaciclib, and causality has been established. Severe (Grade 3 and 4) neutropenia was observed in patients receiving abemaciclib. Patients should be monitored closely for signs of infection, anemia, and bleeding.
Grade 1 or 2	Dose modification not required.
Grade 3	Suspend dose until toxicity resolves to $\leq$ Grade 2. Dose modification not required.
Grade 3, recurrent or Grade 4	Suspend dose until toxicity resolves to $\leq$ Grade 2. Resume at next lower dose.
Requiring administration of blood cell growth factor	Suspend abemaciclib dose for at least 48 hours after the last dose of blood cell growth factor and until toxicity resolves to $\leq$ Grade 2. Resume abemaciclib at next lower dose unless the dose was already reduced for the toxicity that led to the use of the growth factor.

**Table 24. Non-Hematologic Toxicity**

Non-Hematologic Toxicity (excluding diarrhea, hepatotoxicity, and ILD/pneumonitis)	Management
Grade 1 or 2	Dose modification not required.
Persistent or recurrent Grade 2 toxicity that does not resolve with maximal supportive measures within 7 days to baseline or Grade 1	Suspend dose until toxicity resolves to baseline or Grade 1. Resume at next lower dose.
Grade 3 or 4	Suspend dose until toxicity resolves to baseline or Grade 1. Resume at next lower dose.

#### 6.2.1 Condition requiring introduction (unavoidable) of treatment with strong CYP3A inhibitor

Introduction of strong CYP3A inhibitor is subject to discussion and approval of Sponsor-Investigator For all but ketoconazole, reduce abemaciclib to 100 mg BID. In the case of ketoconazole, reduce abemaciclib to 50 mg BID. For patients who have had dose reduction to 100 mg BID due adverse events, dose will be further reduced to 50 mg BID. Subsequently, if the CYP3A inhibitor is discontinued, increase abemaciclib dose (after inhibitor 3-5 half-lives) to the dose that was given prior to starting the inhibitor.

## 7. ADVERSE EVENTS: LIST AND REPORTING REQUIREMENTS

Adverse event (AE) monitoring and reporting is a routine part of every clinical trial. The following list of reported and/or potential AEs (Section 7.1) and the characteristics of an observed AE (Section 7.2) will determine whether the event requires expedited reporting **in addition** to routine reporting.

### 7.1 Expected Toxicities

#### 7.1.1 Abemaciclib

Most common adverse reactions (incidence  $\geq 20\%$ ) are diarrhea, neutropenia, nausea, abdominal pain, infections, fatigue, anemia, leukopenia, decreased appetite, vomiting, headache, alopecia, and thrombocytopenia.

Increases in Serum Creatinine and Renal Insufficiency:

Abemaciclib has been shown to increase serum creatinine due to inhibition of renal tubular transporters without affecting glomerular function (as measured by iohexol clearance). In clinical studies, increases in serum creatinine occurred within the first month of abemaciclib dosing, remained elevated but stable through the treatment period, were reversible upon treatment discontinuation, and were not accompanied by changes in markers of renal function, such as blood urea nitrogen (BUN), cystatin C, or calculated glomerular filtration rate based on cystatin C.

#### 7.1.2 Atezolizumab

Most common adverse reactions ( $\geq 20\%$ ) in patients with locally advanced or metastatic urothelial carcinoma were fatigue, decreased appetite, nausea, constipation, urinary tract infection, diarrhea, and pyrexia. Most common adverse reactions ( $\geq 20\%$ ) in patients with metastatic non-small cell lung cancer were fatigue, decreased appetite, dyspnea and cough.

Atezolizumab has been associated with risks such as the following: IRRs and immune-mediated hepatitis, pneumonitis, colitis, pancreatitis, diabetes mellitus, hypothyroidism, hyperthyroidism, adrenal insufficiency, hypophysitis, Guillain-Barré syndrome, myasthenic syndrome or myasthenia gravis, facial paresis, myelitis, meningoencephalitis, myocarditis, pericardial disorders, nephritis, myositis, and severe cutaneous adverse reactions. In addition, immune-mediated reactions may involve any organ system and may lead to hemophagocytic lymphohistiocytosis (HLH) and macrophage activation syndrome (MAS), which are considered to be potential risks for atezolizumab. Refer to Section 6 of the Atezolizumab Investigator's Brochure for a detailed description of anticipated safety risks for atezolizumab.

### 7.2 Adverse Event Characteristics and Definitions

#### 7.2.1 Adverse Events

An AE is any unfavorable and unintended sign (including an abnormal laboratory finding),

symptom, or disease temporally associated with the use of an investigational medicinal product (IMP) or other protocol-imposed intervention, regardless of attribution.

This includes the following:

- AEs not previously observed in the subject that emerge during the protocol-specified AE reporting period, including signs or symptoms associated with prostate cancer that were not present prior to the AE reporting period.
- Complications that occur as a result of protocol-mandated interventions (e.g., invasive procedures such as cardiac catheterizations)
- If applicable, AEs that occur prior to assignment of study treatment associated with medication washout, no treatment run-in, or other protocol-mandated intervention.
- Preexisting medical conditions (other than the condition being studied) judged by the investigator to have worsened in severity or frequency or changed in character during the protocol-specified AE reporting period.

#### **7.2.2 Serious Adverse Events**

An AE should be classified as an SAE if any of the following criteria are met:

- It results in death (i.e., the AE actually causes or leads to death).
- It is life threatening (i.e., the AE, in the view of the investigator, places the subject at immediate risk of death. It does not include an AE that, had it occurred in a more severe form, might have caused death.).
- It requires or prolongs inpatient hospitalization.
- It results in persistent or significant disability/incapacity (i.e., the AE results in substantial disruption of the subject's ability to conduct normal life functions
- It results in a congenital anomaly/birth defect in a neonate/infant born to a mother exposed to the IMP.
- It is considered a significant medical event by the investigator based on medical judgment (e.g., may jeopardize the subject or may require medical/surgical intervention to prevent one of the outcomes listed above).

#### **7.2.3 Methods and timing for assessing and recording safety variables**

The investigator is responsible for ensuring that all AEs and SAEs that are observed or reported during the study are collected and reported to the FDA, appropriate IRB(s), and Genentech, Inc. in accordance with CFR 312.32 (IND Safety Reports).

#### **7.2.4 Adverse Event Reporting Period**

The study period during which AEs and SAEs, where the patient has been exposed to atezolizumab and/or abemaciclib must be reported. Reporting period begins after informed consent is obtained and initiation of study treatment and ends 30 days following the last administration of study treatment or study discontinuation/termination, whichever is earlier. After this period, investigators should only report SAEs that are attributed to prior study treatment.

#### **7.2.5 Assessment of Severity of Adverse Events**

- **CTCAE term (AE description) and grade:** The descriptions and grading scales found

in the revised NCI Common Terminology Criteria for Adverse Events (CTCAE) version 5.0 will be utilized for AE reporting. All appropriate treatment areas should have access to a copy of the CTCAE version 5.0. A copy of the CTCAE version 5.0 can be downloaded from the CTEP web site  
[http://ctep.cancer.gov/protocolDevelopment/electronic\\_applications/ctc.htm](http://ctep.cancer.gov/protocolDevelopment/electronic_applications/ctc.htm).

The below table should be used for assessing severity for adverse events that are not specifically listed in the NCI CTCAE.

**Table 25. Adverse Event Severity Grading Scale for Events Not Specifically Listed in NCI CTCAE**

Grade	Severity
1	Mild; asymptomatic or mild symptoms; clinical or diagnostic observations only; or intervention not indicated
2	Moderate; minimal, local, or non-invasive intervention indicated; or limiting age-appropriate instrumental activities of daily living a
3	Severe or medically significant, but not immediately life-threatening; hospitalization or prolongation of hospitalization indicated; disabling; or limiting self-care activities of daily living b,c
4	Life-threatening consequences or urgent intervention indicated d
5	Death related to adverse event d

NCI CTCAE = National Cancer Institute Common Terminology Criteria for Adverse Events.

Note: Based on the most recent version of NCI CTCAE (v5.0), which can be found at:  
[http://ctep.cancer.gov/protocolDevelopment/electronic\\_applications/ctc.htm](http://ctep.cancer.gov/protocolDevelopment/electronic_applications/ctc.htm)

a. Instrumental activities of daily living refer to preparing meals, shopping for groceries or clothes, using the telephone, managing money, etc.

b. Examples of self-care activities of daily living include bathing, dressing and undressing, feeding oneself, using the toilet, and taking medications, as performed by patients who are not bedridden.

c. If an event is assessed as a "significant medical event," it must be reported as a serious adverse event

d. Grade 4 and 5 events must be reported as serious adverse events

- **For expedited reporting purposes only:**

- AEs for the agent(s) that are listed above should be reported only if the adverse event varies in nature, intensity or frequency from the expected toxicity information which is provided.
- Other AEs for the protocol that do not require expedited reporting are outlined in the next section (Expedited Adverse Event Reporting) under the sub-heading of Protocol-Specific Expedited Adverse Event Reporting Exclusions.

